PRO00040365: A comparison of the analgesic effects of pectointercostal fascial plane block (PIFB) alone versus PIFB with rectus sheath block (RSB) in cardiac surgery: a prospective, randomized controlled trial.

1. Protocol Title

A comparison of the analgesic effects of pectointercostal fascial plane block (PIFB) alone versus PIFB with rectus sheath block (RSB) in cardiac surgery: a prospective, randomized controlled trial.

NCT04908449

Updated 9.30.2024

PRO00040365: A comparison of the analgesic effects of pectointercostal fascial plane block (PIFB) alone versus PIFB with rectus sheath block (RSB) in cardiac surgery: a prospective, randomized controlled trial.

2. Purpose of the study

To determine if ultrasound-guided bilateral pectointercostal fascial plane blocks with bilateral rectus sheath blocks decrease pain scores, decrease opioid consumption, improve respiratory function, and improve quality of recovery in patients recovering from patients undergoing cardiac surgery in comparison to pectointercostal fascial plane blocks alone.

4. Design and Procedures

This is a single center, prospective, randomized, controlled, double-blinded study. We anticipate recruitment of 50-60 subjects (see #6 Recruitment and Compensation below), with 25-30 in each group. The definitive number will be determined by our final power analysis (see #12 Data analysis and statistical considerations below).

Primary Outcome:

Pain scores on a 0-10 numeric rating scale (NRS) at rest and with deep breathing at 1, 3, 6, 12, 18, and 24 hours post-extubation between subjects receiving PIFB + RSB versus subjects receiving only PIFB.

Secondary Outcomes:

- Total cumulative opioid consumption at 24 and 48 hours post-operatively.
- Change from baseline on incentive spirometry at 1, 3, 12, and 24 hours post-extubation
- Time from ICU arrival to liberation from mechanical ventilation
- ICU and hospital length of stay
- QoR-15 (Quality of Recovery) score²³ 24 hours after extubation

Preoperative Management

Subjects will be randomized on the morning of surgery to receive bilateral PIFB and bilateral RSB with local anesthetic versus bilateral PIFB with local anesthetic and bilateral RSB with saline (placebo).

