Following the informed consent process, a member of the study team will instruct the patient on the appropriate use of incentive spirometry at the bedside and correct performance will be assessed. Three measurements will then be recorded to provide a baseline of incentive spirometry function.

Intraoperative Management

All subjects will receive the standard of care anesthetic regimen for their cardiac surgery, with specific medications at the discretion of their attending anesthesiologist, with the following exceptions:

- Fentanyl and sufentanil will be the only narcotics used intraoperatively.
- Fentanyl administration will be limited to bolus dosing, rather than infusions.
- Any sufentanil infusions must be stopped prior to or upon arrival in the intensive care unit.
- Sufentanil dosing range will be within 0.2-0.5 mcg/kg/hr. Extubation in the operating room is at the discretion of the attending anesthesiologist.
- Furthermore, neuromuscular blockade will be reversed prior to handoff in the ICU.

Postoperative Management

PRO00040365: A comparison of the analgesic effects of pectointercostal fascial plane block (PIFB) alone versus PIFB with rectus sheath block (RSB) in cardiac surgery: a prospective, randomized controlled trial.

Each PIFB will be performed with 15 mL of 0.25% bupivacaine with 5 mcg/ml of epinephrine, and bilateral RSB will be performed with an additional 20 mL of 0.25% bupivacaine with 5 mcg/ml of epinephrine (10mL on each side).

Single injection pectointercostal fascial plane blocks

The ultrasound-guided pectointercostal fascial plane blocks will be performed as follows:²⁰ a linear high frequency ultrasound probe will be placed in a parasagittal orientation between the third and fourth ribs, approximately one centimeter lateral to the sternal border, and all relevant structures will be identified, including the pectoralis major muscle, ribs, intercostal muscles, pleura, and any vasculature, including the internal mammary artery and vein. Color doppler will be used confirm the location of vasculature.

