Again, all nerve blocks will be performed by an anesthesiologist experienced in regional anesthesia and/or a trainee supervised by an anesthesiologist experienced in regional anesthesia.

Postoperative Evaluation

Evaluation of acute postoperative pain intensity using a 0-10 numeric rating scale (NRS) will be undertaken at the following time points, both at rest and with deep breathing:

PRO00040365: A comparison of the analgesic effects of pectointercostal fascial plane block (PIFB) alone versus PIFB with rectus sheath block (RSB) in cardiac surgery: a prospective, randomized controlled trial.

- 1, 3, 6, 12, 18, and 24 hours post-extubation

Incentive spirometry will be assessed at 1, 3, 12, and 24 hours post-extubation, with three measures taken at each time point in order to compare postoperative performance with baseline spirometry.

Review of the medical chart will be made post-operatively to gather other data, including total intraoperative oral morphine equivalent consumption, cumulative opioid consumption at 24 and 48 hours, time from ICU arrival to tracheal extubation, length of stay in the ICU, length of stay in the hospital, administration of other analgesic or sedating medications in the first 48 hours after extubation, and QoR-15 (Quality of Recovery) score²² administered 24 hours after extubation (with margin of error of 18-30 hours to avoid waking patients in the middle of the night). Occurrences of any adverse events reported by the subject or medical team will also be collected.

Collect additional surgical data: intraoperative OME, total surgical time, total cardiopulmonary bypass time, and total aortic crossclamp time. It is important to collect this data in order to control for these elements, as it is known that longer cardiopulmonary bypass time and aortic crossclamp time are associated with longer time to extubation and longer ICU length of stay²³.

5. Selection of subjects

Criteria for inclusion:

- Subjects scheduled for elective cardiac surgery involving primary median sternotomy and subxiphoid chest tube placement
- Age 18-85 years of age
- BMI 18-50 kg/m²
- Weight > 60 kg

Criteria for exclusion:

- Left ventricular ejection fraction (LVEF) < 30%
- Preoperative, intraoperative, or immediate post-operative placement of intra-aortic balloon pump or deployment of extra-corporeal membrane oxygenation (ECMO)
- Inability to understand or speak English
- Allergy to bupivacaine or other amide local anesthetic

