- Contraindication to peripheral nerve block (e.g. local infection, previous trauma to the block site)
- Chronic opioid consumption (daily oral morphine equivalent of >20 mg) in the past three months
- Severe pulmonary or hepatic disease
- Neurological deficit or disorder
- Suspected or known addiction to or abuse of illicit drug(s), prescription medicine(s), or alcohol within the past two years
- Uncontrolled anxiety, schizophrenia, or other severe psychiatric disorder
- Patients who remain intubated for >24 hours after the stop of anesthesia will be removed from the study

6. Subject recruitment and compensation

Participating cardiac surgeons will share a basic study information sheet with potential subjects in their pre-operative surgery clinic visit. Potential subjects (see inclusion criteria above) will be identified on the surgical schedule by a member of the study team, typically at least one day in advance of the surgical procedure. These individuals will be contacted by telephone or in-person, if they are pre-admitted, and asked for permission to discuss the study. The purpose of the study will be explained, the consent form

PRO00040365: A comparison of the analgesic effects of pectointercostal fascial plane block (PIFB) alone versus PIFB with rectus sheath block (RSB) in cardiac surgery: a prospective, randomized controlled trial.

read out loud, and any questions answered. Potential subjects will be encouraged to take time to discuss the study with family and will be told that there will be additional time to answer any questions on the day of surgery (or date prior, if pre-admitted). Potential subjects will be told that there is no obligation to take part in the study and their decision will not affect the quality of their care.

On the day of surgery or day prior to surgery (if pre-admitted), one of the investigators will approach the potential subject in his/her hospital room or the preoperative area, as appropriate, and answer any remaining questions. Subjects that indicate their interest in participating will then sign an informed consent and complete a HIPAA authorization form. There will be no compensation for subjects for their participation.

7. Consent process

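### Removing patients still intubated at 24 hours, after randomization, cuts off the ventilation-time outcome near its own value and probably drops long ICU stays; secondary outcomes only, size unknown

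*Combined protocol and SAP*

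**What the plan says.** The removal rule is the last item under the exclusion criteria in Section 5: "Patients who remain intubated for >24 hours after the stop of anesthesia will be removed from the study". Its clock starts at the stop of anesthesia.

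Section 4, Preoperative Management, sets the time of allocation: "Subjects will be randomized on the morning of surgery to receive bilateral PIFB and bilateral RSB with local anesthetic", against the same blocks with saline in the rectus sheath. The block is described under Postoperative Management ("bilateral RSB will be performed with an additional 20 mL of 0.25% bupivacaine"), with no clock time relative to ICU arrival or extubation.

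The secondary outcomes in Section 4 include "Time from ICU arrival to liberation from mechanical ventilation" and "ICU and hospital length of stay". Under Postoperative Evaluation, the items taken from chart review include "time from ICU arrival to tracheal extubation, length of stay in the ICU, length of stay in the hospital". The same part collects bypass and crossclamp times and explains why: "It is important to collect this data in order to control for these elements", because "longer cardiopulmonary bypass time and aortic crossclamp time are associated with longer time to extubation and longer ICU length of stay".

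Section 12 covers a chart review of pain scores and opioid use to support the power analysis, and then power for the pain outcomes. It defines no analysis set, gives no rule for data from removed patients, and names no method for ventilation time or length of stay.

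**The concern.** Although listed as an exclusion criterion, the rule cannot be applied until about a day after surgery, when the patient is already randomized. That the block has normally been given by then is an inference from the heading under which it is described.

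The rule and the ventilation outcome both end at extubation and start at neighbouring events (stop of anesthesia, ICU arrival). Removing a patient for passing 24 hours on one clock therefore deletes a value of about 24 hours or more on the other. The outcome loses its upper tail.

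Length of stay is affected less directly. By the protocol's own account, long bypass and crossclamp times go with both late extubation and long ICU stay, so the removed patients are likely to be long-stay patients in the ICU. The protocol does not say this of hospital stay, where the same effect is plausible but unstated.

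At stake is the randomized comparison on these outcomes. If the added block shortens ventilation, fewer active than control patients pass 24 hours, and the patients left in the two arms are no longer comparable. Blinding does not prevent this, because the imbalance would come from the treatment effect itself.

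**Working it through.** **Plan's own figures.** The plan gives none for ventilation time, stay or expected removals. Its 24 and 29 patients per group (0.9 and 0.8 SD, alpha 2.5%, 80% power) concern pain. The two-sided normal approximation gives 24 and 30, close to those figures, but they do not bear on this point.

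**How many removals.** The documents give no rate. If 2%, 5% or 10% of patients stay intubated beyond 24 h, the expected number removed is 1.0, 2.5 or 5.0 of 50, and 1.2, 3.0 or 6.0 of 60. The chance of at least one removal, 1 − (1 − p)^N, is 64%, 92% or 99.5% for N = 50 and 70%, 95% or 99.8% for N = 60.

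**Effect of truncation. All inputs are assumed:** ventilation time is lognormal with control median m and log-SD s; active times are 0.75 × control; the two clocks are treated as equal. For an arm with median M:

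- a = (ln 24 − ln M)/s; proportion removed = 1 − Φ(a)
- full mean = M·exp(s²/2); mean after removal = full mean × Φ(a − s)/Φ(a)
- median after removal = M·exp(s·Φ⁻¹(0.5·Φ(a)))

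Worked case, m = 8 h and s = 0.9:

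- Control: a = 1.0986/0.9 = 1.221, so 11.1% are removed.
- Active (median 6 h): a = 1.3863/0.9 = 1.540, so 6.2% are removed. Of 30 per arm, that is 3.3 against 1.9.
- Full means are 11.99 and 9.00 h, a difference of 3.00 h.
- After removal they are 8.44 and 7.09 h, a difference of 1.36 h, which is 45% of the true difference.

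| Control median, log-SD | Removed, control v active | Median difference, full → after removal | Mean difference, full → after removal |
|---|---|---|---|
| 6 h, 0.6 | 1.0% v 0.3% | 1.50 → 1.46 h (97%) | 1.80 → 1.62 h (90%) |
| 6 h, 0.8 | 4.2% v 1.8% | 1.50 → 1.34 h (89%) | 2.07 → 1.42 h (69%) |
| 8 h, 0.8 | 8.5% v 4.2% | 2.00 → 1.59 h (80%) | 2.75 → 1.52 h (55%) |
| 8 h, 0.9 | 11.1% v 6.2% | 2.00 → 1.46 h (73%) | 3.00 → 1.36 h (45%) |

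On the rank scale the loss is smaller. The excess of P(active < control) over 0.5 is kept at 98%, 94%, 89% and 86.5% in the four cases. Simulated Mann-Whitney power at 30 per group (10,000 runs) goes from 41.6% to 40.7%, 25.3% to 22.1%, 26.2% to 20.2% and 21.3% to 15.7%.

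**No effect on ventilation.** Both arms lose the same proportion and the expected difference stays zero; simulated rejection after truncation is 4.6–5.4%.

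**Covariate adjustment.** Suppose bypass and crossclamp times explain 10–30% of the variance of log ventilation time (assumed). Adjusting for them raises the share of the log-scale ventilation effect kept only from 74–96% to 76–97%. Adjustment can reduce bias in stay, but it does not restore deleted ventilation times.

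**Primary pain outcome.** With an assumed correlation of 0.2–0.5 between pain and log ventilation time, the shift is 0.004–0.041 SD, against a design difference of 0.8–0.9 SD.

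**The case against.** The strongest objection is that the size rests wholly on assumptions. The documents give no distribution of ventilation time, no late-extubation rate and no expected effect on ventilation, and both arms receive the active chest-wall block. Several features may shorten the tail: surgery is elective, low ejection fraction and severe lung or liver disease are excluded, sufentanil infusions end by ICU arrival, and extubation in the operating room is allowed. The lognormal model has no mass at zero for patients extubated in the operating room. The upper cases, with 8.5–11.1% of controls beyond 24 h, have no support in the text; the mildest case keeps 90% or more on every scale. All of this stands, and it limits the severity.

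It is also true that removal from the study need not mean that collected data are discarded. The text does not say. Removal from analysis is the likely reading because nothing provides for keeping the data, but it remains a reading.

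A reader might infer more than the documents support:

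- **That the rule can reverse the sign of the ventilation effect.** This needs an effect concentrated in long ventilation times. If only times above 24 h were cut by 25%, a true mean benefit of 0.08–1.12 h would appear as a harm of 0.10–0.64 h. Nothing in the documents suggests that pattern, and Mann-Whitney rejection would still be only about 5–6%.
- **That it undermines the primary result.** The pain shift above is small.
- **That the opioid outcome, or the exclusions for balloon pump or ECMO, carry the same bias.** No such bias has been shown.

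**Conclusion.** The point holds for the secondary outcomes. As written, and on its likely reading, the rule truncates ventilation time at about 24 h after randomization and drops patients likely to have long ICU stays. Any effect on hospital stay is plausible only.

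Whether there is bias depends on whether the added block changes ventilation time. If it shortens ventilation proportionally, the comparison is pulled toward no effect. The table shows how far under assumed inputs, and those ranges illustrate the mechanism; they do not estimate what this trial will see. If the block leaves ventilation unchanged, the cost is lost numbers. The loss of power is 1–6 percentage points on a comparison that would have only 21–42% power under the same assumptions.

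Severity is minor to moderate. The case for acting is that the defect is clear from the text and cheap to remove, not that a large bias has been demonstrated.

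**What to change.** In Section 5, replace removal with a statement that patients intubated beyond 24 hours after the stop of anesthesia are retained in their randomized group for ventilation time and for ICU and hospital stay. In Section 12, state that ventilation time is analysed in all randomized patients by a rank-based or time-to-event method with no cut at 24 hours. Report by arm how many patients were intubated beyond 24 hours.

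The cost is wording. Extubation time and both stays already come from chart review, so no new data collection is needed. The downside is a slightly larger variance for stay, since the long-stay patients are back in. The change concerns data handling only and leaves clinical management as it is.

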Our data analysis plan is as follows: since we had no pilot data on AUC pain outcomes, we considered a conservative scenario when the two outcomes are uncorrelated and described detectable differences between study outcomes in terms of standard deviations (SDs). To evaluate power properties of the Hotelling T2 at $\text{ALPHA} = 5\%$ test, we considered statistical power of two two-sample t-tests at $\text{ALPHA} = 2.5\%$. At 24 patients per group, the detectable at 80% power difference between group means = 0.9 SDs ($\text{ALPHA} = 2.5\%$). If the normality assumption is violated, Mann-Whitney test will have the same power properties at 25 patients per group. At 29 patients per group, the detectable at 80% power difference between group means = 0.8 SDs ($\text{ALPHA} = 2.5\%$); Mann-Whitney nonparametric alternative will have the same power properties at 30 patients per group.

13. Data & Safety Monitoring

In accordance with federal regulations the PI will monitor for, review, and promptly report to the IRB, appropriate institutional officials, sponsor, coordinating center and the appropriate regulatory agency head all unanticipated problems involving risks to subjects or others that occur in the course of a subject's participation in a research study, all AE reports will be reported per the MCW IRB policies. PI will be monitoring all AEs and submitting reports to the IRB per MCW IRB policy.

Furthermore, an independent monitor has been chosen for the study, and this individual is a regional anesthesiologist, who will not be involved in study proceedings but who will be updated on study progress as per the DSMP.

14. Privacy, Data Storage and Confidentiality

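### Section 12 reports single t-test power as Hotelling T2 power and calls uncorrelated outcomes conservative without saying which outcomes shift; the 80% sits 2.5 to 4 points above the T2 floor

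*Combined protocol and SAP*

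**What the plan says.** Section 4 (Design and Procedures) gives the primary outcome as "Pain scores on a 0-10 numeric rating scale (NRS) at rest and with deep breathing at 1, 3, 6, 12, 18, and 24 hours post-extubation". It says "We anticipate recruitment of 50-60 subjects", in two equal groups of 25 to 30, and leaves the definitive number to the power analysis in section 12.

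Section 12 (Data analysis and statistical considerations) gives that analysis in standard deviation units, "since we had no pilot data on AUC pain outcomes". It says "we considered a conservative scenario when the two outcomes are uncorrelated". It continues: "To evaluate power properties of the Hotelling T2 at" 5%, "we considered statistical power of two two-sample t-tests at" 2.5%. Two results follow:

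- "At 24 patients per group, the detectable at 80% power difference between group means = 0.9 SDs"
- "At 29 patients per group, the detectable at 80% power difference between group means = 0.8 SDs"

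The section does not name the two outcomes, does not say whether the difference applies to one or both, considers no correlation other than zero, and gives no power computed for T2 itself.

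**The concern.** The power of a bivariate T2 test depends on the correlation between the outcomes and on how the effect is split between them. A single t-test's power depends on neither. Replacing one by the other hides the quantity that the word *conservative* is about.

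The primary outcome suggests that the two outcomes are the rest and deep-breathing AUCs, measured in the same patients at the same times. A positive correlation is then the natural expectation. If both outcomes move together, correlation costs T2 power, so zero correlation is the favourable end of the plausible range. Because this paragraph is meant to fix the sample size, its figures should belong to the test it names and its label should point the right way.

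**Working it through.** **Inputs.** From section 12: T2 at 5%; t-tests at 2.5%; correlation 0; 0.9 SD with 24 per group; 0.8 SD with 29 per group; target 80%. From section 4: equal groups. Assumptions: T2 is the intended test, two-sided t-tests, bivariate normal data, common covariance, no dropout. No document gives a correlation, so a range is shown.

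**Step 1: reproduce the plan's figures.** For a single two-sided t-test at 2.5% the noncentrality is d√(n/2).

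- 24 per group, 0.9 SD: 0.9 × √12 = 3.118. Power is 81.0% by normal approximation and 78.5% by the exact noncentral t.
- 29 per group, 0.8 SD: 0.8 × √14.5 = 3.046. Power is 79.0% by normal approximation and 76.9% exactly.

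The printed figures are therefore single-test figures, near 80% by normal approximation. The exact 80%-detectable differences are 0.915 and 0.828 SD. One-sided tests at 2.5% would give 86.3% and 84.9%, so the two-sided reading fits better.

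**Step 2: power of T2.** With two outcomes, T2 is referred to F on 2 and 2n − 3 degrees of freedom. For shifts d1 and d2 in SD units and correlation ρ, the noncentrality is

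λ = (n/2)(d1² − 2ρ·d1·d2 + d2²)/(1 − ρ²).

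**Step 3: both outcomes shift by d.** Then λ = n·d²/(1 + ρ), which falls as ρ rises. At ρ = 0, λ is 24 × 0.81 = 19.44 and 29 × 0.64 = 18.56.

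| ρ | 24 per group, 0.9 SD | 29 per group, 0.8 SD |
|---|---|---|
| 0 | 97.6% | 97.1% |
| 0.5 | 88.6% | 87.5% |
| 0.8 | 81.9% | 80.5% |
| 0.9 | 79.7% | 78.2% |

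Simulation with 40,000 replicates gave 97.5% and 97.2% at ρ = 0. For 80% power, the required number per group rises from 14 (ρ = 0) to 25 (ρ = 0.9) at 0.9 SD, and from 17 to 31 at 0.8 SD.

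**Step 4: only one outcome shifts.** Then λ = (n/2)d²/(1 − ρ²), smallest at ρ = 0, where it is 9.72 and 9.28. T2 power is 77.5% and 76.0%. At ρ = 0.8 it is 99.7% and 99.6%. The 80%-detectable differences at ρ = 0 are 0.93 and 0.84 SD.

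**Step 5: unequal shifts.** If the second shift is k times the first (0 < k < 1), λ is smallest at ρ = k, where it again equals (n/2)d². The floor is therefore the same 77.5% and 76.0%. Power is not monotone in ρ: for k = 0.5 and 24 per group it is 86.4% at ρ = 0, 77.5% at 0.5, 86.4% at 0.8 and 96.4% at 0.9. Zero correlation beats a positive ρ only below 2k/(1 + k²), here 1/1.25 = 0.8.

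**Step 6: split the gap to 80%.**

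- 24 per group: 80 − 78.5 = 1.5 points from rounding or approximation in the t-test figure; 78.5 − 77.5 = 1.0 point from using a t-test in place of T2.
- 29 per group: 80 − 76.9 = 3.1 points; 76.9 − 76.0 = 0.9 point.

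**The case against.** The strongest defence is that the plan never says both outcomes shift by the stated amount. If only one does, zero correlation is the worst case and *conservative* is the right word. There is also a sense in which the alpha split is conservative: two independent tests at 2.5% have a familywise error of 1 − 0.975² = 4.94%, so halving alpha is nearly exact without correlation and stricter than needed with positive correlation. Finally, the t-test is a close stand-in for the T2 worst case (78.5% against 77.5%, and 76.9% against 76.0%), and 0.93 and 0.84 SD still round to the printed 0.9 and 0.8.

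All of this stands as a limit on the size of the point. It does not rescue the paragraph. On the one-outcome reading the label is right but T2 power is not 80%. On the equal-shift reading the 80% greatly understates power at zero correlation, and the label is wrong. The alpha argument concerns error control for a pair of t-tests, whereas the section claims to describe T2 power.

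A reader might infer that zero correlation is always the most favourable case. Steps 4 and 5 show otherwise, and a negative correlation would be more favourable still (99.7% at ρ = −0.3 with equal shifts and 24 per group). Nor do the documents set a rule for winning on either or both t-tests, so power under such rules is not relevant.

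**Conclusion.** The point holds, at minor severity. Section 12 gives single t-test power as the power of Hotelling T2, and its label for the uncorrelated case is correct or incorrect according to an assumption it does not state. No reading makes that case both conservative and 80% powered for T2.

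The stated 80% exceeds the T2 floor by 2.5 points (24 per group) or 4 points (29 per group), with about 1 point due to the substitution. The floor assumes that the larger of the two shifts is the stated one. At the planned 25 per group and 0.9 SD the floor is 79.4%.

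Two stronger conclusions are not supported. The trial is not shown to be materially underpowered: with equal shifts and little correlation the plan understates its power. Nor does the plan promise at least 80% in every case; that would be read into one word. The identity of the two outcomes is inferred from the primary outcome, and their positive correlation is an expectation, not a documented figure.

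**What to change.** In section 12:

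1. Name the two outcomes and state the assumed shift on each, in SD units.
2. Remove *conservative*, or limit it to the case where only one outcome shifts.
3. Replace the t-test calculation with T2 power from the noncentral F distribution at correlations 0, 0.5, 0.8 and 0.9.
4. Quote the worst-case 80%-detectable differences to two decimals: 0.93 SD at 24 per group and 0.84 SD at 29 per group.

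The cost is one small table and a few sentences. Recruitment does not change; the stated worst-case figure becomes slightly less favourable.
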